1.1 Primary Objectives

1.11 To assess safety of delivering MRI-guided prostate SBRT in patients with metastatic prostate cancer.

Treatment will be deemed safe if there is no more than 3 acute >G3 likely radiation treatment related GI/GU toxicity within 3-6 months after treatment (CTCAE 5.0 criteria) completion. Given that the treatment plans will meet rigorous normal tissue constraints used for standard prostate SBRT that have been established now with up to 10 year follow up data in patients with localized prostate cancer, we do not anticipate any increased toxicity on this study for metastatic prostate cancer patients.

1.2 Secondary Objectives

1.21 We will measure quality of life (HRQOL) using: 1) the Expanded Prostate Cancer Index Composite (EPIC-26) short form questionnaire, 2) I-PSS. QOL assessments will occur at baseline, 3-6 months, and at 9-12 months. Toxicity data will be measured with CTCAE 5.0 at 3-6 months, and at 9-12 months.

1.3 Correlative Study Objectives

1.31

To collect complete blood count (CBC) measurements at baseline, post-treatment and 3-6 month followup to assess impact of SBRT on immune correlates and neutrophil lymphocyte ratios.

To describe gut microbiome changes (abundance, composition, diversity) associated with prostate radiation.

2 BACKGROUND

2.1 *Radiation to the prostate: Rationale for treating patients with metastatic prostate cancer*

Next to skin cancer, prostate cancer is the most commonly diagnosed cancer in men, and second leading cause of cancer death.⁴ It is estimated that one out of seven men will be diagnosed with prostate cancer during their lifetime. Due to improvements in diagnostic imaging, monitoring and therapy, an increasing number of patients are being diagnosed with early metastatic prostate cancer, where an aggressive approach is hypothesized to yield improved clinical outcomes.

The appropriate management of patients with metastatic prostate cancer has varied widely and continues to evolve. In the past, local therapy to the prostate (radical prostatectomy, definitive external beam radiation (EBRT)) was offered only to patients with non-metastatic prostate cancer, and systemic therapies such as androgen deprivation therapy (ADT) was administered to patients with disease outside of the prostate. However, new data suggests that treatment of the primary tumor provides clinical benefit to men with metastatic disease.^{5,6}

The STAMPEDE (Radiotherapy to the Primary Tumour for Newly Diagnosed, Metastatic Prostate Cancer) trial results demonstrate that select men with metastatic prostate cancer derive an overall survival benefit from prostate-directed EBRT. In this randomized controlled phase 3 study, men with newly diagnosed metastatic prostate cancer were treated with either standard of care, or standard of care plus prostate EBRT. The primary outcome was overall survival. With median follow up of 37 months, it was reported that patients with metastatic prostate cancer had improved overall survival after prostate EBRT versus none, 3 year OS 81% vs 73% (HR 0.68, 95% CI 0.52-0.90, P=0.007). Based on these results, prostate EBRT has become a standard treatment option for patients with low metastatic burden prostate cancer.⁵ Low metastatic burden prostate cancer is defined using the CHARTED (Chemohormonal Therapy in Metastatic Hormone Sensitive Prostate Cancer) and STAMPEDE trial criteria: any metastatic prostate cancer that does not have a) visceral metastases AND/OR b) four or more bone metastases with one or more outside the vertebral bodies or pelvis. Any patients without a) or b) are considered to have low metastatic burden.^{5,7} Furthermore, there is retrospective data suggesting that prostate RT improves outcomes in men with metastatic prostate cancer who do not necessarily fit the definition of low metastatic burden.³²⁻³³

In the STAMPEDE study, patients receiving EBRT were allowed either 20 fractions of radiation to 55 Gy over 4 weeks, or 6 fractions of radiation to 36 Gy over 6 weeks. Neither of these regimens are commonly utilized in the United States. Stereotactic body radiation therapy delivers 36.25 Gy over 5 fractions in 1-2 weeks, completing treatment in a short span of time with a low overall adverse event rate demonstrated in patients with non-metastatic prostate cancer¹⁻³. In this study, we hope to demonstrate the safety and feasibility of delivering SBRT in patients with metastatic prostate cancer, using MR-guided treatment delivery.

2.2 Prostate cancer radiotherapy: Rationale for extreme hypofractionation SBRT

In the past, standard fractionation EBRT was delivered over 9-10 weeks, with 1.8 to 2.0 Gy administered daily, in up to 50 treatment sessions. The inconvenience associated with the protracted length of a standard course of prostate treatment has stimulated interest in delivering more radiation dose per session, to reduce the duration of treatment. Compared to conventional fractionation, hypofractionation (higher dose of radiation given in fewer sessions) allows for reduced number of treatment visits, increasing patient convenience while lowering health care costs. This has resulted in the development of extremely hypofractionated regimens, delivered most commonly within 5 fractions, allowing completion of treatment generally within 1-2 weeks. Such treatments are delivered using stereotactic or image-guided IMRT approaches, most commonly referred to as prostate stereotactic body radiation therapy (SBRT).

Single institutional and pooled reports have demonstrated similar efficacy and toxicity to conventionally fractionated regimens.¹⁻³ The NCCN treatment paradigm currently includes SBRT as an alternative to conventionally fractionated regimens at centers with appropriate technology, physics and clinical expertise.⁸ SBRT enables patients to undergo a non-invasive treatment and be finished in five treatments, achieving outcomes equivalent to long-course EBRT or surgery, without a surgical procedure, general anesthesia and the risk of associated complications. As such, it is an excellent option to deliver prostate EBRT in patients with metastatic prostate cancer.

2.3 Biological rationale for SBRT

Proponents of prostate cancer hypofractionation argue that the rectum and bladder are less sensitive to increases in dose per fraction than prostate cancer and that therefore hypofractionation should yield negligible increases in late toxicity while providing improved cancer control. The α/β is a theoretical measure of a tissue's predicted response to a dose of radiation, relative to the size of the dose delivered per fraction. Conventional daily doses of radiation are based on the presumed high α/β ratios of most malignant tumors. Higher α/β ratios mean that tumor response is less dependent on the amount of radiation administered with each fraction when compared to adjacent normal tissue, and therefore that a lower radiation dose per treatment can typically be used. Lower tumor α/β ratios mean that a larger dose of radiation per treatment can provide improved efficacy in terms of therapeutic ratio, tumor control versus risk of complications. A large body of work theorizes that the α/β for prostate cancer is low (~1.5), implying that a hypofractionated schedule could improve prostate cancer control, while maintaining a low risk of severe normal tissue complications (see Table 1).⁹ The radiobiological linear-quadratic cell survival model was used to calculate the biologically equivalent doses for tumor control and complications to normal organs, using standard 2 Gy fractions delivered five times a week.¹⁰⁻¹²

Table 1. Equivalent total doses in 2 Gy per fraction (EQD2) based on α/β Biologically Effective Doses (BED)

	α/β (Gy)	EQD2 Standard (1.8 Gy x 45 fx)	EQD2 SBRT (7 Gy x 5 fx)	EQD2 SBRT (7.5 Gy x 5 fx)	EQD2 SBRT (8 Gy x 5 fx)	EQD2 SBRT (8.5 Gy x 5 fx)	EQD2 SBRT (9 Gy x 5 fx)
Total Dose (Gy)		81	35	37.5	40	42.5	45
Tumor	1.5	76.37 Gy	85 Gy	97.65 Gy	110 Gy	123.07 Gy	135 Gy
Fibrosis/stricture	2	76.95 Gy	78.75 Gy	89.06 Gy	100 Gy	111.56 Gy	123.7 Gy
Telangiectasia	4	78.3 Gy	64.17 Gy	71.88 Gy	80 Gy	88.54 Gy	97.5 Gy
Rectum	4	78.3 Gy	64.17 Gy	71.88 Gy	80 Gy	88.54 Gy	97.5 Gy
Bladder	4	78.3 Gy	64.17 Gy	71.88 Gy	80 Gy	88.54 Gy	97.5 Gy

2.4 SBRT Outcomes

To date, results from prospective and retrospective studies demonstrate good biochemical control and low toxicity for SBRT, with commonly used doses ranging from 35-45 Gy in 5 fractions (see Table 2). Randomized data from the phase III PACE trial, comparing standard fractionation EBRT to 78 Gy or moderately hypofractionated EBRT to 62 Gy, versus SBRT to 36.25 Gy in 5 fractions, show no difference in grade 2 or higher acute urinary or bowel toxicity, suggesting SBRT to be a well-tolerated, safe alternative to longer treatment regimens.¹³

SBRT compares favorably to outcomes for standard fractionation EBRT to 81 Gy, which has 10-year biochemical RFS of 91%, 78% and 62%, respectively, for low-, intermediate- and high-risk prostate cancer, and late Grade 3 gastrointestinal (GI) and genitourinary toxicity of 1% and 5%, respectively.¹⁴ There is a lack of consensus regarding the appropriate dose to use for prostate SBRT. Extrapolating from dose escalation studies in conventionally fractionated EBRT,^{15,16} a higher dose in SBRT is hypothesized to result in improved local control. However, delivery of higher dose results in small but significant increase in GU toxicity. Katz and [name] showed significantly higher late grade 2-3 GU toxicity with 36.25 Gy compared to 35 Gy (13.2 vs 8.8%, P<0.05). With 35 Gy in five fractions, the majority of toxicity was grade 2, and overall toxicity was low without impacting GU quality of life. As shown in Table 2, late grade 3 GU/GI toxicity after SBRT appears to be comparable to that of conventionally fractionated EBRT, ranging from 0.6 – 3%^{1,3} with longest median follow-up of 7 years.

Table 2. Biochemical control after prostate SBRT. *prospective

Study	SBRT Dose (5 fx)	FU	# Pts	Risk Categories	bPFS	Toxicity ≥3
Bolzicco ^{17*}	35 Gy	36m	71	Low (41%), Int (42%), High (17%)	3y 94.4%	GI 0%, GU 1%
King ^{18*}	35-36.25 Gy	5y	41	Low, Favorable Int Risk	5y 92.7%	GI 0%, GU 3.5%
McBride ^{19*}	36.25-37.5 Gy	44.5 m	45	Low	3y 97.7%	GI 4.4%, GU 2.2%
Madsen ^{20*}	33.5 Gy	41m	40	Low	4y 90%	GI 0%, GU 0%
Fuller ^{21*}	38 Gy/ 4 fx	60m	259	Low (43%), Int (57%)	5y Low 100%, Int 88.5%	GI 0%, GU 3.1%

Kim ²²	45-50 Gy	42m	47	Low (38%), Int (62%)	4y 98%	GI 0%, GU 0%
Loblaw ^{23*}	35 Gy	55m	84	Low	5y 98%	GI 1%, GU 1%
Mantz ^{24*}	40 Gy	60m	102	Low, Fav Int	5y 100%	GI 0%, GU 0%
Chen ²⁵	35-36.5 Gy	2.3y	100	Low (37%), Int (55%), High (8%)	2y 99%	GI 0%, GU 1%
Katz and [name] ²	35-36.25 Gy	72m	477	Low (68%), Int (32%)	7y Low 95.6%, Fav Int 93.5%, Unfav Int 79.3%	GI 0%, GU 2%
Katz and [name] ²⁶	35-36.25 Gy	84m	515	Low (63%), Int (30%), High (7%)	8y Low 93.6%, Int 84.3%, High 65.0%	GI 0%, GU 2%
Katz ²⁷	35-36.25 Gy	108m	230	Low	10y 93%	GI 0%, GU 2%

Abbreviations: FU, follow up; Gy, Gray; Fx, fractions; m, months; y, years; IQR, interquartile range

*SBRT monotherapy patients

** Heterogeneous SBRT planning such that at least 1% of PTV receives $\geq 150\%$ of prescription dose.

2.5 *Rationale for Simultaneous Integrated Boost*

Both EBRT and SBRT target the entire prostate gland with radiation. Studies on patterns of failure following conventional EBRT demonstrate that 85-100% of local failures occur in the region of macroscopic tumor.^{28,29} Modern treatment planning systems have the ability to selectively target visible lesions within the prostate to a higher dose, resulting in heterogeneous dose distributions that target high-risk nodules to increased dose and surrounding prostate to a lower dose. A phase II trial is currently ongoing in the Netherlands (Hypofractionated focal lesion ablative microboost in prostate cancer, “hypo-FLAME” NCT02853110), to look at feasibility of a focal ablative boost with SBRT, using dose of 35 Gy in 5 fractions with a boost to visible nodules up to 50 Gy. Furthermore, our department has a currently ongoing investigator initiated protocol in patients with non-metastatic prostate cancer (“MRI-guided Stereotactic Body Radiotherapy (SBRT) with Simultaneous Integrated Boost for Prostate Cancer” PI: [name], [name] IRB Protocol # 1802019010), which utilizes a simultaneous integrated boost in patients with non-metastatic prostate cancer, and has demonstrated the feasibility and safety of such an approach in 9 patients who have thus far enrolled. The dose used for simultaneous integrated boost in this protocol, 40 Gy, remains within the acceptable range of doses for prostate SBRT.

2.6 *Need for IGRT in prostate radiotherapy*

SBRT delivers high dose to the target with a rapid dose fall-off. Thus, it is important to account for prostate motion as much as possible during treatment delivery (intrafraction motion), and between each treatment fraction (interfraction motion). A small shift in the prostate, if unaccounted for, can result in significantly decreased dose to the target. Position changes are inevitable due to bowel gas/stool fluctuation, bladder filling and/or prostate edema from radiation.³⁰ There are multiple techniques to account for prostate motion during delivery of SBRT. Such techniques include tracking via implanted radiofrequency transponders (e.g., Calypso), on-board kV imaging of prostate fiducials at 30-60 second intervals (e.g., Cyberknife), and use of multiple cone-beam CTs during treatment. Traditional image-guided radiation is unable to provide real-time feedback of target position. Treating multiple radiation targets (prostate, seminal vesicles, high-risk nodules) with steep dose gradients becomes particularly challenging with standard image guidance systems, because adjustments are made offline or at prolonged select intervals during treatment delivery.

2.7 ViewRay: a unique radiation delivery approach

The ViewRay MRIdian Linac system is a radiation delivery machine that integrates a linear accelerator with real-time MRI imaging. The ViewRay machine allows fusion of MR imaging with treatment planning. The uniqueness of this approach is the image guided delivery component, based on precise MRI-based detection of target and normal tissue during treatment in real-time. The ViewRay will provide real-time MRI imaging to ensure that the high-dose region is precisely targeted. MRI guided radiation has the benefit of not requiring fiducial implantation or excess radiation exposure from multiple cone beam CT. Furthermore, motion monitoring can be performed with images acquired up to 4 frames a second, allowing live feedback of treatment position.

ViewRay offers the ideal system for delivery of prostate SBRT, due to its ability to provide image guidance “live”, during treatment. Real-time MRI imaging allows superior soft-tissue differentiation with excellent visualization of the prostate. This ViewRay platform offers the ideal setting for this study, that aims at precisely delivering prostate SBRT with a simultaneous integrated boost to visible nodules. MRI guided radiation, a property unique to ViewRay, will be exploited in the current trial to deliver precise treatment with resultant lower dose to surrounding normal structures.

The goal of this study is to assess safety of treating patients with metastatic prostate cancer with MRI-guided prostate SBRT. Safety is defined as lack of more than 3 patients with treatment related acute >G3 GI or GU toxicity within 3- 6 months post treatment. The proposed SBRT dose (36.25 Gy in 5 fractions to the whole prostate) has been reported in the literature to be safe and well tolerated (Table 2), with no acute G3 toxicity. The proposed boost dose to 40 Gy in applicable patients is within the range of current standard of care SBRT doses, and is also expected to be well-tolerated. Furthermore, it has been tested in our currently ongoing investigator initiated protocol in patients with non-metastatic prostate cancer (“MRI-guided Stereotactic Body Radiotherapy (SBRT) with Simultaneous Integrated Boost for Prostate Cancer” PI: [name], [name] IRB Protocol # 1802019010). As of 4/29/19, 15 patients with localized prostate cancer have enrolled on this study with planned accrual of 30 patients, and have demonstrated excellent safety and feasibility with boost doses up to 45 Gy. It

is therefore expected that similar outcomes can be achieved in patients with metastatic prostate cancer, though it is possible that the addition of systemic therapy may alter likelihood of toxicity.

2.8 Rationale for Correlative Studies Background: Microbiome and blood sample collection

Patients accrued to the study will donate a stool specimen and a blood sample both before and after radiation, to study their changes in the microbiome and circulating immune correlates during and after radiotherapy, and at 3-6 month follow up.

Preliminary results from our ongoing study “Effect of Radiotherapy Variables on Circulating Effectors of Immnue Response and Local Microbiome” PI: [name], IRB Protocol #: 1708018471 demonstrate depletion of circulating lymphocytes in prostate cancer patients undergoing protracted standard radiation compared to 5-fraction SBRT (which is the regimen we will use on this study) (results submitted to ASTRO). We will study this phenomenon further in patients undergoing SBRT on this study. We have also found a temporary increase in neutrophil:lymphocyte ratio (NLR) during radiation to the prostate in our dataset of patients; patients enrolled on this protocol will also have assessment of NLR at baseline, after RT and at 3-month follow up.

The host microbiome is an emerging topic of investigation, with growing evidence that commensal microbiota impacts anti-tumor immune response, and sensitivity to systemic therapies and immunotherapy. Commensal bacteria outnumber human cells by at least 10-fold, colonizing host mucosal surfaces and playing critical roles in metabolism, defense against pathogens, and crosstalk between the environment and immune system. Preclinical studies suggest that microbiota impact the immune system through a number of mechanisms, including possible modulation of myeloid-derived cells; stimulation of T helper cells, and enhancement of memory T-cell response. Dysbiosis, or shifts in microbial composition, may modulate response to cancer therapy. We hypothesize that the underlying microbial community composition will be impacted by administration of radiation to the prostate. Our preliminary data in mice suggests fluctuations in composition, abundance and diversity after local tumor-directed radiation. We hope to explore this further in patients who are undergoing SBRT by collecting microbiome samples at baseline, upon completion of RT, and at follow up.

3 SUBJECT SELECTION

3.1 Study Population

Men with a histologically confirmed diagnosis of metastatic prostate adenocarcinoma, meeting the inclusion and exclusion criteria below, and electing to undergo definitive radiation treatment with SBRT, will be eligible for participation in this study.

3.2 Inclusion Criteria

1. Biopsy-proven diagnosis of prostate adenocarcinoma
2. Age ≥ 18
3. Must have metastatic prostate cancer proven on biopsy or imaging

3.3 Exclusion Criteria

1. History of prior pelvic radiation (external beam or brachytherapy)
2. Inability to undergo MRI
3. AUA score >20
5. For patients on systemic therapy, enrollment must be within six months of start of therapy unless exception is made by protocol PIs (Drs. [name], [name] or [name])

4 REGISTRATION PROCEDURES

4.1 Patient Registration

Before any protocol specific procedures can be carried out, investigators/staff will fully explain the details of the protocol, the study procedures and the aspects of patient privacy regarding research information. Patients will be provided a comprehensive explanation of the proposed treatment including the type of therapy, the rationale for treatment on the protocol, alternative treatments that are available, any known adverse events, the investigational nature of the study and the potential risks and benefits of the treatment. The informed consent document will meet all requirements of the Institutional Review Board (IRB). All subjects/patients are informed in the consent that participation or refusal to participate in the research study will not affect any of the clinical treatment or services to which they would otherwise be entitled.

The physicians who may obtain informed consent are listed on the title page of this protocol. The informed consent form will be signed by the participant and the registering physician. Once signed, a copy will be given to the patient and one will be maintained with the patient's medical record. Once eligibility is confirmed and informed consent is documented, the patient will be registered by the study coordinator/data manager.

Patients will be centrally registered with the Office of Billing Compliance. To register a patient, submit the following documents via the JIRA Registration Process:

- Legible copy of the HRBAF
- Signed informed consent

Registration must be completed within 24 hours of the signing of informed consent.

5 STUDY PROCEDURES

	Pre-Study	Fx 1	Fx2	Fx 3	Fx 4	Fx 5*	Post-RT Visits (3-6 months, 9- 12 months s/p RT)
Informed consent	X						
Demographics	X						
PSA	X						X
Acute/Late Toxicity Assessment (CTCAE)	X					X	X
EPIC-26, I-PSS	X						X
Imaging: Planning CT/MR;	X						
Blood draw and microbiome sample	X					X	X**

** no blood draw at 9-12 months.

5.1 Pre-Study Visit

At the initial screening visit, patient will undergo:

- Informed consent
- Medical history
- Baseline EPIC-26 Questionnaire, I-PSS forms

5.2 Imaging Studies

Placement of a rectal spacer is optional. Treatment planning CT and MR will be performed with appropriate immobilization. Patients will be advised to drink approximately 1-2 cups of water 1 hour prior to the CT simulation to allow for a comfortably full bladder, if tolerated; this will be modified according to physician's discretion. A radiation planning MR will be obtained at the physician's discretion.

5.3 Radiation Treatment Planning

5.3.1 Contours

The prostate +/- seminal vesicles (SV) will be contoured as the clinical target volume (CTV) as per usual practice. For patients with identifiable dominant intraprostatic nodules (**Select PIRADS 3-5 and/or PSMA avid (if PSMA PET/MR is available) and/or biopsy positive nodules (chosen based on physician's clinical judgment and correlation with biopsy findings)**), there is the option for DIN to be contoured as gross tumor volume(s) (GTV). There will be no planning target volume (PTV) expansion for the DIN GTV. The PTV expansion for the CTV will be 0-5 mm on the prostate, depending on physician discretion as per standard care.

The rectum will be drawn from the bottom of the ischial tuberosities to the sigmoid flexure. The urethra will be delineated on MRI from the prostatic apex, to entry of urethra into the penile bulb, using a 5-6 mm brush.

The bladder, femoral heads, penile bulb will also be contoured as normal structures.

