5.3.2 Dose/Treatment Planning Parameters

The CTV (prostate +/- SV) will be treated to dose of 36.25 Gy in 5 fractions. For patients with identifiable DINs, at the physician's discretion, there is an option for a simultaneous integrated boost to PIRADS 3-5 or PSMA avid nodules and/or biopsy positive nodules, delivering 40 Gy to the contoured nodule(s) as a mean dose while respecting normal tissue constraints to rectum and urethra. (If normal tissue constraints to the rectum and urethra can not be achieved, the DIN will be boosted to a lower dose, or not boosted)

Volume of the PTV receiving prescribed SBRT dose should ideally be $\geq 95\%$; acceptable suggested deviation is dose $>85\%$

Critical organ limits (SBRT monotherapy):

1. Rectum: Maximum dose to 1 cc 38.5 Gy, Max dose to 3 cc 34.4 Gy, Max point dose 40 Gy. Acceptable deviation is maximum dose to 1 cc 39 Gy, max dose to 3 cc 36 Gy and max point dose of 42 Gy.
2. Bladder: Maximum dose to 1 cc 38.5 Gy, Max point dose 40 Gy. Acceptable deviation is max point dose of 42 Gy.
3. Penile Bulb: No more than 105% of prescription dose; D3cc 25 Gy. This is a soft constraint.
4. Femoral heads: Maximum point dose 30 Gy
5. Small bowel: Maximum point dose 25 Gy
6. Urethra: Max dose 40 Gy. Will allow up to 42 Gy point dose. Urethra planning organ at risk volume (PRV) can be created around the contoured urethra if there is uncertainty

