10 MEASUREMENT OF EFFECT

This is a safety study.

Treatment will be deemed safe if there are no more than 3 acute greater than grade 3 radiation treatment related GI/GU adverse events within 3-6 months of treatment (CTCAE 5.0 criteria).

The primary endpoint will be safety, as measured by the percentage of treatments that are delivered without radiation treatment related GI/GU toxicity within 3-6 months from start of treatment. Given that the treatment plans will meet standard normal tissue constraints used for SBRT, and rigorous safety metrics need to be met before radiation is delivered, we do not anticipate any increased toxicity on this study compared to standard SBRT.

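### Section 5.3.1 as written contours the urethra only below the prostate, so apart from the apical margin the prostatic urethra lies outside the structure whose dose limit decides the 40 Gy boost

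*Combined protocol and SAP*

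**What the plan says.** Section 5.3.1 (Contours) gives the urethral structure two explicit ends: "The urethra will be delineated on MRI from the prostatic apex, to entry of urethra into the penile bulb, using a 5-6 mm brush". Apart from the rectum, which has its own instruction, the remaining organs at risk are listed in one sentence: "The bladder, femoral heads, penile bulb will also be contoured as normal structures". The target margin is also set there: "The PTV expansion for the CTV will be 0-5 mm on the prostate".

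Section 5.3.2 (Dose/Treatment Planning Parameters) prescribes 36.25 Gy in 5 fractions to the prostate, with or without seminal vesicles. It allows an optional boost of 40 Gy to visible or biopsy-positive nodules, "as a mean dose while respecting normal tissue constraints to rectum and urethra". If the limits fail, the consequence is stated: "If normal tissue constraints to the rectum and urethra can not be achieved, the DIN will be boosted to a lower dose, or not boosted". The urethral limit reads "Urethra: Max dose 40 Gy. Will allow up to 42 Gy point dose". A urethral planning risk volume (PRV) is optional and "can be created around the contoured urethra if there is uncertainty".

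Section 10 bases its expectation of no added toxicity on constraint compliance: "Given that the treatment plans will meet standard normal tissue constraints used for SBRT".

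**The concern.** The boost target is inside the prostate. A urethral limit guards against boost dose only if the urethra near the nodule belongs to the structure from which the dose is read. As written, Section 5.3.1 removes most of that length from the structure that Section 5.3.2 relies on, so the two sections do not fit together.

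Two things are at stake. The first is the planning rule: taken literally, it lets a boost go ahead after a urethral check made largely below the gland. The second is what can later be said about the plans. Genitourinary toxicity is part of the primary endpoint, and Sections 1.1 and 10 both argue from plans meeting normal tissue constraints. A plan could be recorded as meeting the urethral limit without the urethra beside a boosted nodule having been examined.

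**Working it through.** The plan gives no figure to reproduce on this point. The check sets the two sections side by side and adds a little dose arithmetic for scale.

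**1. Extent of the contour.** Section 5.3.1 runs from the apex to the penile bulb. The apex is the lower end of the gland and the bulb lies below it; this is general anatomy, which the documents do not spell out. The length from bladder neck to apex is therefore outside the written contour.

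**2. Location of the boost.** Section 5.3.1 describes the boosted nodules as intraprostatic. Most such nodules would lie above the start of the contour. An apical nodule would lie beside its upper end.

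**3. Whether anything else covers the missing length.**
- The other contoured organs are rectum, bladder, femoral heads and penile bulb. None is the prostatic urethra.
- The bladder limits in Section 5.3.2 (38.5 Gy to 1 cc, 40 Gy point) may protect tissue near the bladder neck, but do not cover the urethra within the gland.
- The PRV is optional and is built around the same contour. It might reach a few millimetres above the apex, and no further.
- For the CTV, Section 5.3.1 defers to usual practice. It does not do so for the urethra.
- None of the change summaries corrects the wording.

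**4. How much of the written contour lies in the target.** The margin is 0 to 5 mm. If the CTV ends at the apex (an assumption), at most about the first 5 mm of the written contour lies in the PTV.

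**5. Share of the constraint set.** Section 5.3.2 lists six organ limits (rectum, bladder, penile bulb, femoral heads, small bowel, urethra), and one is affected. Two of them (rectum, urethra) decide the boost, and one of those two is affected.

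**6. Dose scale, using Section 5.3.2 values.**
- Urethral maximum minus gland prescription: 40 − 36.25 = 3.75 Gy. As a ratio, 40 / 36.25 = 110.3%.
- Point allowance over prescription: 42 / 36.25 = 115.9%.
- Point allowance over boost mean: 42 / 40 = 105.0%.

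The boost value of 40 Gy is a mean in the nodule. Unless the dose there is uniform, part of the nodule receives more than 40 Gy, and no nodule maximum is stated. The urethral limit could therefore bind next to a nodule. Whether it would do so in a given patient depends on the distance from nodule to urethra, which the documents do not give. These ratios show where the check matters. They do not estimate any excess dose.

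**7. Number of plans.** The number boosted and the contours actually drawn are not reported. The number of affected plans could be anything from 0 to the accrual ceiling of 25, so no useful estimate is possible.

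**The case against.** The strongest reply is that the intent is plain. A urethral condition on an intraprostatic boost makes little sense unless the urethra in the gland is assessed, so apex reads as a one-word slip. Section 5.3.2 also states its limit for the urethra without confining it to the drawn segment; only the PRV sentence refers to the contour. The slip is indeed likely. But a maximum dose is read from a drawn structure, and Section 5.3.1 is the only instruction on how to draw it. The wording needs correcting even if planners understood what was meant.

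The second reply is that little turns on it now. The version 5.0 summary says the study is closed to accrual. Section 12 plans no dosimetric or constraint-compliance analysis. The primary endpoint is observed CTCAE toxicity, which is recorded whatever was contoured. Section 2.7 places 40 Gy within standard SBRT doses and reports good safety in a related departmental protocol with boosts up to 45 Gy. All of this stands. It limits the consequence and argues against re-contouring every delivered plan.

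A third reply concerns apical nodules: they lie beside the start of the contour and may be partly covered. That also stands, and the point is limited accordingly.

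A reader might go further and infer that the boost mean of 40 Gy against a urethral maximum of 40 Gy leaves no headroom. That compares a mean in one structure with a maximum in another. It would describe headroom only if the urethra received the nodule mean, and nothing in the documents shows that it did.

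**Conclusion.** The inconsistency is real as written. Apart from the apical margin, the prostatic urethra is not in the structure to which the 40 Gy maximum and 42 Gy point allowance apply, although that limit helps decide whether a nodule is boosted. No effect in patients is shown.

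The conclusion rests on the anatomical order of apex and bulb, and on reading Section 5.3.1 literally. A reader might infer that patients were boosted with the intraprostatic urethra unchecked, that urethral doses exceeded the limit, or that the trial's safety conclusion is unsound. The documents support none of these. They contain no contours, urethral doses or nodule distances, and planners may well have drawn the full urethra. The grade 4+ decision depends on observed events, and no change to it is claimed. What remains is a planning instruction that needs correcting, and a limit on what may be said about urethral compliance.

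**What to change.** Reword the urethral sentence in Section 5.3.1 along these lines: *Contour the urethra on MRI starting at the bladder neck, continuing through the whole prostate and ending where it enters the penile bulb (brush width unchanged). The 40 Gy maximum and the 42 Gy point allowance apply to this full length.*

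With accrual closed, the amendment corrects the record and any later use of the text, but protects no new patient. If a report states that plans met the urethral limit, make that claim only for patients whose contour on file includes the prostatic urethra. Routine re-contouring of all delivered plans is not required.

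The cost is a short text amendment. If compliance is to be reported, planning staff would also need to look at the stored contours, at most 25. Section 11.4 keeps study data for at least 5 years after termination; that this includes plans and contours is an assumption. No patient contact is needed, and the endpoint, sample size and decision rule stay as they are.
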